#### **3.2.2. Treatment Experience Assessed using DCOA 2 Questionnaire**

*Proportion of Subjects/Caregiver Dyads that select the weekly injection schedule compared to the daily injection schedule in each of the domains below as assessed by the DCOA 2 Questionnaires completed at Week 24:*

- *Choice of injection pen (1 question);*
- *Preferred injection schedule (1 question);*
- *Convenience of injection schedule (1 question);*
- *Easier to follow (1 question);*

- *Pen ease of use* (4 questions);
- *Patient life interference* (6 questions);
- *Caregiver life interference, including family life interference* (11 questions);
- *Benefit relating to the injection schedule* (1 question);
- *Intention to comply* (4 questions).

### **3.2.3. Patient Global Impression Severity-Impact on Daily Activities (PGIS-IDA)**

*The PGIS-IDA at baseline and at the end of each period (Week 12 and Week 24) – 1 question, 7-point scale.*

### **3.3. Other Endpoint(s)**

Subject compliance is defined as  $\geq 80\%$  adherence to injections.

### **3.4. Baseline Variables**

No variables require specific definitions for baseline.

As this is a cross-over study with no washout period after the end of treatment period I and before the start of treatment period II, baseline is calculated as the last pre-dose assessment prior to administering the study drug at Baseline/Visit 1 (Study Day 1 Week 0).

### **3.5. Safety Endpoints**

The following safety endpoints will be analyzed in the study:

- *Frequency, severity, and relationship of adverse events to somatrogon;*
- *Serious adverse events;*
- *Discontinuations due to adverse events;*
- *Frequency and severity of abnormal lab values;*
- *Detection of anti-rhGH antibodies (and neutralizing antibodies);*
- *Detection of anti-somatrogon antibodies (and neutralizing antibodies).*

For the analysis of safety endpoints, the programming standards defined in Pfizer CDISC Safety Rulebook will be followed. Missing dates for study medication, and adverse events (AE's) will be imputed as implemented within the CaPS algorithms with the exception of vital signs which are shown below.

For Vital Signs:

The following out of expected ranges will be used to identify potential values of clinical concern for the vital signs parameters in reporting the summaries and shift tables where appropriate.

Test	Low Range	High Range
Respiratory rate (breaths/min)	10	40
Heart Rate (beats/min)	50	135
Systolic BP (mm Hg)	80	130
Diastolic BP (mm Hg)	40	90
Body temperature (oC)	35	38

**3.5.1. Adverse Events**

An adverse event is considered treatment emergent relative to a given treatment if:

- The event occurs for the first time during the effective duration of treatment and was not seen prior to the start of treatment (for example, during the baseline or run-in period), or
- The event was seen prior to the start of treatment but increased in severity during treatment.

The effective duration of treatment is determined by the lag time. Any event occurring within the lag time of 7 days, whether this occurs during a break in treatment or at the end of treatment, is attributed to the corresponding treatment period.

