3. STUDY DESIGN

The study is a randomized, open-label, multi-center, 2-period crossover in children 3 to <18 years of age with GHD. The planned study duration is 24 weeks with a screening period of up to 30 days and a follow-up phone call four weeks after the last clinic visit. Approximately 90 children with GHD who have been stable on treatment with daily Genotropin[®] for a minimum of 3 months will be enrolled. Subjects will be randomized to one of two sequences, either 12 weeks of continued treatment with daily Genotropin[®] followed by 12 weeks of treatment with weekly somatrogon, or 12 weeks of treatment with weekly somatrogon followed by 12 weeks of treatment with daily Genotropin[®] (see Figure 2 below). There will be no treatment wash-out period since these subjects must take growth hormone continually. Subjects will have study visits at Baseline, Weeks 6, 12, 18, and 24. Subjects will also be followed up by phone 8-12 days after each treatment period begins (Week 1 and Week 13). Subjects and caregivers (as a Dyad) will complete the DCOA questionnaires at baseline and at the end of each 12 week treatment period (DCOA 1 at baseline and after Period I and Period II; DCOA 2 after Period II). Subjects and caregivers will also complete the PGIS-IDA at baseline and after Period I and Period II. [Appendix 5](#) describes which sub-group (subject and/or caregiver) completes which part of the questionnaire and at which time point. All subjects/caregivers will receive a follow up phone call at Week 28.

Figure 2. Study Design

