8.1.4. Time Period for Collecting AE/SAE Information

The time period for actively eliciting and collecting AEs and SAEs (“active collection period”) for each subject begins from the time the subject provides informed consent, which is obtained before the subject’s participation in the study (ie, before undergoing any study-related procedure and/or receiving investigational product), through and including a minimum of 28 calendar days after the last administration of the investigational product.

For subjects who are screen failures, the active collection period ends when screen failure status is determined.

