### 6.2.4. Safety Endpoints

The following safety endpoints will be summarized descriptively in each treated group using the Safety population as described in [Section 4](#).

- Frequency, severity, and relationship of adverse events to somatrogon;
- Serious adverse events;
- Discontinuations due to adverse events;
- Frequency and severity of abnormal lab values;
- Detection of anti-rhGH antibodies (and neutralizing antibodies);
- Detection of anti-somatrogon antibodies (and neutralizing antibodies).

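### SAP 3.5.1 has no treatment-emergence rule fitted to a crossover: read literally, it leaves Period II recurrences at the same or lower severity out of the AE tables, and its 7-day lag overlaps the next product

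*SAP*

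**What the plan says.** SAP 3.5.1 opens with "An adverse event is considered treatment emergent relative to a given treatment if" and gives two alternative conditions. The first is "The event occurs for the first time during the effective duration of treatment and was not seen prior to the start of treatment", with the illustration "for example, during the baseline or run-in period". The second is "The event was seen prior to the start of treatment but increased in severity during treatment". It then adds a lag rule: "Any event occurring within the lag time of 7 days, whether this occurs during a break in treatment or at the end of treatment" is credited to the corresponding treatment period.

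Four other parts of the plan bear on how this works:

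- **Design.** Protocol 3 describes a two-period crossover and states "There will be no treatment wash-out period since these subjects must take growth hormone continually". Protocol 4.3 randomizes 1:1 to the two sequences.
- **Collection.** Under Protocol 8.1.4, active AE collection "for each subject begins from the time the subject provides informed consent". Events on pre-study daily growth hormone are therefore on record before Day 1.
- **Use.** The first safety endpoint in SAP 6.2.4 is "Frequency, severity, and relationship of adverse events to somatrogon". SAP 6.6.1 reports it as the number and percentage of subjects with treatment-emergent events, by relatedness and severity.
- **Switching.** Protocol 5.5 puts the last Genotropin dose 36 ± 24 hours before the first somatrogon dose in Sequence 1. In Sequence 2 the last somatrogon dose falls 7 days ± 72 hours before the first Genotropin dose.

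**The concern.** In a parallel-group trial, time before treatment is time off study drug, so excluding events already seen removes background illness. In a crossover, time before the second product includes twelve weeks on the first. If the rule looks back over those weeks, whether an event counts for somatrogon depends on the period in which somatrogon was given.

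The events most exposed are those that come and go with injections. Protocol 1.5 names injection site reactions as a potential risk for all subjects. Protocol 8.2.2.1 records high symptom scores as AEs once for each treatment, so one child can generate the same AE on both products. The safety objective is purely descriptive. A tabulated incidence that is too low is therefore an error in the result itself.

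**Working it through.** The documents give no AE incidence, recurrence rate or severity mix, so there is no plan figure to reproduce on this point. The check applies the rule to a case, then derives the loss for assumed values.

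**1. The rule applied.** A child has a mild injection-site event in Period I. It resolves, and it returns, still mild, in Period II.

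- Period I product: first occurrence, not seen before, so emergent.
- Period II product, per-treatment reading: Period I precedes the start of this product, so the first condition fails. Severity did not rise, so the second fails. The event is not emergent. A milder recurrence fares the same.
- An event that simply continues from Period I without worsening is also excluded, and rightly so. Only new episodes are lost.
- If the start of treatment means Day 1, the recurrence was not seen before that point. But the first condition also demands a first occurrence during treatment. The recurrence meets both parts only if treatment means the Period II product in one clause and all study treatment in the other.

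**2. Size for one event term.** Assume 1:1 sequences and no period effect. Let

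- p = true per-period incidence on the product,
- q = probability of a new episode in Period II given one in Period I,
- s = probability that the recurrence is not more severe.

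Half of a product's exposure is in Period I and is counted in full. The Period II half loses p·q·s. With equal incidence on both products:

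counted = p/2 + p(1 − q·s)/2 = p(1 − q·s/2)

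The relative loss is q·s/2 overall, and q·s within Period II. All values below are assumptions.

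| p | q | s | counted | relative loss |
|---|---|---|---|---|
| 10% | 10% (independent) | 1 | 9.5% | 5% |
| 10% | 30% | 0.8 | 8.8% | 12% |
| 10% | 50% | 1 | 7.5% | 25% |
| 40% | 80% | 0.8 | 27.2% | 32% |
| 10% | 80% | 1 | 6.0% | 40% |

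The loss is zero if events never recur and cannot exceed 50%. In 90 subjects, the third row means 9.0 expected against 90 × 0.075 = 6.75 counted.

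A simulation with three severity grades and 30% incidence on each product agrees. It counts 26.5% with independent recurrence, about 24% when 52% recur, and 21.3% when 70% recur.

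**3. Effect on the contrast.** More generally, each product loses P(event in both periods, Period II episode not more severe)/2. Suppose true incidences of 40% and 20%, with 15% having such a pair. Then 40 − 7.5 = 32.5% and 20 − 7.5 = 12.5%. The difference stays at 20 points; the ratio moves from 2.0 to 2.6. In the simulation, where severity varies, 40% and 20% become 35.1% and 14.5%, a difference of 20.6 points. The risk difference is thus close to preserved, and exactly so only when severity patterns match.

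**4. The lag at the switch.**

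- Genotropin to somatrogon: the gap is 12 to 60 hours, or 0.5 to 2.5 days. The lag runs 7 − 2.5 = 4.5 to 7 − 0.5 = 6.5 days past the first somatrogon dose.
- Somatrogon to Genotropin: the gap is 4 to 10 days. The lag runs from 7 − 4 = 3 days into Genotropin to 7 − 10 = −3, that is, it ends 3 days before the first Genotropin dose.

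A reaction to the first somatrogon injection in Sequence 1 therefore falls inside Genotropin's lag. No rule says which product it belongs to.

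**The case against.** The strongest reply is that the text is ambiguous, not wrong. The only earlier phases it names are baseline and run-in; Period I is not mentioned. SAP 3.4 and 3.5.2 fix a single baseline at Day 1 because there is no washout. The SAP does not say whether an event means a coded term or a separate AE record; if each new record is a new event, nothing is lost. The operative rule may sit in the sponsor's safety rulebook and reporting standards, cited in SAP 3.5 and 6.6.1, which are not in the documents. All of this stands as a limit on certainty. It does not rescue the plan, because the single-baseline statements cover baseline variables and laboratory data, not AEs, and the Day 1 reading needs treatment to change meaning mid-sentence.

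It is also fair that the raw information survives. SAP 5 lists all data. Protocol 8.2.2.1 captures injection-site reactions four ways, and SAP 6.2.1 compares the DCOA 1 symptom scores by treatment without any emergence flag. But none of these corrects the tables in SAP 6.6.1 that report the safety endpoint.

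Three stronger inferences should be resisted:

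- **That the missing washout causes the loss.** Period I precedes Period II with or without one. The short gap matters only for the lag overlap.
- **That both products' reported rates are certainly too low.** The literal reading undercounts recurrences on both, but the lag can credit early somatrogon events to Genotropin, so Genotropin's net direction is uncertain.
- **That the comparison of products is distorted.** The SAP plans no relative risk and no AE hypothesis test, and the risk difference is largely kept.

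**Conclusion.** The point holds as a defect in one definition. On its literal reading, SAP 3.5.1 undercounts per-term incidence in the Period II half of each product's data; on other readings, it leaves Period II recurrences undefined. The illustrative loss is about 5% relative for a 10% event recurring independently and about 12–40% for strongly recurrent events (q from 0.3 to 0.8, s from 0.8 to 1). These figures rest on assumed recurrence and severity, 1:1 sequences and no period effect.

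They apply term by term. In a row for any AE the loss is smaller, because a subject with a different emergent Period II event is still counted. The lag overlap is a separate gap with its own uncertain direction. The matter is worth settling before the flag is programmed; it does not touch the primary endpoint.

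**What to change.** Rewrite SAP 3.5.1 by period:

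- An event is emergent for a product if, during that product's period, a new episode starts or an ongoing event worsens relative to its status at that period's first dose. A resolved earlier episode does not disqualify it.
- Exclude only events that are ongoing at that first dose and do not worsen.
- For attribution, end the Period I lag at the first Period II dose, so that each event goes to one product. State where an event goes if it falls after the 7-day lag but before that dose.
- Tabulate treatment-emergent events by treatment, and by period within treatment. SAP 5 already allows summaries by period.

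The cost is a paragraph of SAP text, one changed derived flag and some extra table columns. The downside is that recurrent background events will count in both periods, so both products' rates will look slightly less favourable. In return, an event's counting for somatrogon no longer depends on the period in which somatrogon was given.

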1.5. Benefits and Risks of Participation

The benefit of participation for all subjects in this study is close monitoring of the safety of the treatment and of their medical condition. The experience to date is that somatrogon has an efficacy and safety profile similar to that of Genotropin®. There is, however, limited experience in switching patients from treatment with Genotropin® to somatrogon. A potential risk of participation for all subjects is the occurrence of injection site reactions.

Additional information for this compound may be found in the single reference safety document (SRSD), which, for this study, is the Sponsor provided IB. The SRSD for the comparator agent is the local product documents (LPD).

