5.5. Switching between Genotropin[®] and Somatrogon

- Subjects that will be switching from Genotropin[®] to somatrogon in Sequence 1 should administer their final injection of Genotropin[®] 36 hours (± 24 hours) prior to their first injection with somatrogon; their somatrogon dose will be based on their weight (rounded to the nearest tenth) taken at baseline/Visit 1.
- Subjects that will be switching from somatrogon to Genotropin[®] in Sequence 2 should administer their final injection of somatrogon 7 days (± 72 hours) prior to their first injection with Genotropin[®].
- Subjects in Sequence 1 that have completed the study should restart their regularly prescribed supply of Genotropin[®], Humatrope[®], (USA only) or Omnitrope[®] (USA only) 7 days after their final somatrogon injection. Their Genotropin[®], Humatrope[®] (USA only), or Omnitrope[®] (USA only) dose should be the same dose that they were receiving at the end of Period I unless directed otherwise by their provider.
- Subjects in Sequence 2 that have completed the study should restart their regularly prescribed supply of Genotropin[®], Humatrope[®], (USA only) or Omnitrope[®] (USA only) 24 hours after their last study dose of Genotropin[®] was received. Their Genotropin[®], Humatrope[®], (USA only) or Omnitrope[®] (USA only) dose should be the same dose that they were receiving at the end of the study unless directed otherwise by their provider.

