6.1. Screening

6.1.1. Visit Days -30 to 0

The Screening Visit will occur 0 to 30 days prior to the Baseline/Randomization Visit. The following procedures and assessments will be performed during this visit:

- Obtain written informed consent – the investigator will obtain a written informed consent from each subject before any trial related activity is initiated. If the subject consents to the investigator contacting their primary care provider, the investigator should ascertain that the subject's primary care provider has been informed of the subject's participation in the trial and that safety will be monitored;
- Verify trial eligibility by checking and documenting inclusion and exclusion criteria ([Sections 4.1](#) and [4.2](#));
- Register subjects with IRT. The IRT must be contacted before screening assessments begin in order to obtain a subject screening identification number (SSID);
- Obtain and record demographics and general medical history;

- Measure and record vital signs: heart rate, temperature, respiratory rate and blood pressure ([Section 7.2.2](#));
- Measure and record body weight and body height;
- Conduct complete physical examination ([Section 7.2.4](#));
- Obtain and record prior medications and instruct subjects on the use of concomitant medications ([Section 5.8](#)).
- Collect fasting (10 hours) specimens for laboratory exams:
 - Blood for fasting lipid profile, hematology with differential, blood chemistry, liver function tests, free thyroxine (FT4), IGF-I, IGF-I SDS, hemoglobin A1c, somatrogon level, anti-somatrogon Ab (and neutralizing Ab), and anti-rhGH Ab (and neutralizing Ab);
 - Urine for urinalysis;
 - Urine for pregnancy test (women of child bearing potential (WOCBP)).
- Provide contraception recommendations ([Section 4.4.1](#));
- Inquire for and record adverse events;
- Inform subject/caregiver of date of next visit;
- Instruct all subjects to administer their final injection of Genotropin[®], Humatrope[®] (USA only), or Omnitrope[®] (USA only) 36 hours (± 24 hours) prior to their next visit (Visit 1).

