- Conduct contraception check ([Section 4.4.1](#));
- Collect all used and unused study medication containers (drug accountability);
- Collect all used and unused cartridges and/or injection devices (drug accountability);
- Review and collect subject diary;
- Injection site assessment;
- Inquire for and record adverse events;
- Inquire for and record injection device complaints;
- Collect fasting (10 hours) specimens for laboratory exams:
 - Blood for fasting lipid profile, hematology with differential, blood chemistry, liver function tests, FT4, IGF-I, IGF-I SDS, hemoglobin A1c, somatrogon level and anti-somatrogon Ab (and neutralizing Ab) (only for subjects who have been on somatrogon for the previous 12 weeks of treatment), and anti-rhGH Ab (and neutralizing Ab);
 - Urine for urinalysis;
 - Urine for pregnancy test (WOCBP).
- Questionnaire Administration:
 - Provide DCOA1 questionnaire and train Subject/Caregiver Dyad on completion;
 - Subject/Caregiver Dyad completes DCOA1 questionnaire;
 - Subject/Caregiver Dyad completes PGIS-IDA question;
 - Clinical Site Staff completes DYAD Questionnaire.
- Drug dispensation and dosing:
 - Confirm for subjects switching from Genotropin[®] to somatrogon that it has been 36 hours (± 24 hours) since their most recent injection of Genotropin[®] relative to this visit;

- Confirm for subjects switching from somatrogon to Genotropin[®] that it has been 7 days (± 72 hours) since their most recent injection of somatrogon relative to this visit;
- Dispense new study treatment based on randomization;
- Instruct subject on injection;
- Subject will inject study treatment;
- Instruct/provide subjects with a new subject diary corresponding to the treatment they are switching to.
- Assessments during and after subject injection:
 - Injection site assessment;
 - Inquire for and record adverse events;
 - Inquire for and record injection device complaints;
 - Inform subject/caregiver of date of next visit and required dates of administration of study drug.

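### The 7-day adverse event lag in SAP 3.5.1 does not end when the next study drug starts, so early somatrogon events in Sequence 1 could be counted under Genotropin

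*SAP*

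**What the plan says.** SAP 3.5.1 judges treatment emergence separately for each treatment. An event qualifies if it first occurs within that treatment's effective duration and "was not seen prior to the start of treatment (for example, during the baseline or run-in period"), or if it was already present and became more severe. The lag sets the effective duration: "Any event occurring within the lag time of 7 days", the section says, "whether this occurs during a break in treatment or at the end of treatment, is attributed to the corresponding treatment period". It does not say from what point the 7 days are counted, or what happens if the other study drug starts before they are over.

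The relevant design features are these:

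- Protocol 3: there is no washout between periods.
- Protocol 5.5, Sequence 1: the last Genotropin injection is 36 h (±24 h) "prior to their first injection with somatrogon".
- Protocol 5.5, Sequence 2: the last somatrogon injection is 7 days (±72 h) "prior to their first injection with Genotropin".
- Protocol 5.4 and 6.2.4: the first Period II dose is given in clinic at Visit 4. Adverse events and the injection site are checked before it and again under "Assessments during and after subject injection".
- SAP 6.5.3: treatment duration is last dose date minus first dose date, plus 1 for Genotropin and plus 7 for somatrogon.
- SAP 6.2.4 and 6.6.1: safety endpoints are summarised descriptively by treatment, without hypothesis tests.

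**The concern.** A post-treatment lag suits a trial in which treatment ends and nothing follows. Here the second drug starts inside the lag of the first. The SAP adapts its baseline definition to the missing washout (3.4 and 3.5.2), but the lag rule, which stands between those sections, has no such adaptation.

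The safety objective is to describe the safety and tolerability of somatrogon, so the per-drug counts of treatment-emergent events are the safety result. In Sequence 1 the overlap falls on the first somatrogon dose. Protocol 1.5 notes that experience of switching from Genotropin to somatrogon is limited, and states: "A potential risk of participation for all subjects is the occurrence of injection site reactions". A reaction seen at Visit 4 after the first somatrogon injection is first-dose information, and the text allows it to appear in the Genotropin column.

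**Working it through.** The plan gives no overlap figure to reproduce, so the check starts from its lag and its switching windows.

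**Inputs.** Lag 7 days = 168 h (SAP 3.5.1). Gap between last dose of the old drug and first dose of the new one: Sequence 1, 36 ± 24 h = 12 to 60 h; Sequence 2, 168 ± 72 h = 96 to 240 h (Protocol 5.5). Allocation 1:1 (Protocol 4.3) of about 90 subjects (Protocol 9.1), so about 45 per sequence. Each period lasts 12 weeks = 2,016 h.

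**Lag counted from the last dose.** Overlap after the first dose of the new drug = max(0, 168 − gap).

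| Sequence | Gap (h) | Overlap (h) | Share of the 2,016 h period |
|---|---|---|---|
| 1, Genotropin to somatrogon | 12 / 36 / 60 | 156 / 132 / 108 | 7.7% / 6.5% / 5.4% |
| 2, somatrogon to Genotropin | 96 / 168 / 240 | 72 / 0 / 0 | 3.6% / 0 / 0 |

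The longest permitted Sequence 1 gap (60 h) is well short of 168 h, so every Sequence 1 subject who switches within the window has an overlap. It covers 64% to 93% of the first weekly somatrogon interval (108/168 to 156/168; 79% nominal). Over both sequences this is 2.7% to 3.9% of all somatrogon time (3.3% nominal), but it includes the first somatrogon dose of up to 45 of 90 subjects. First somatrogon doses in Sequence 2 are not affected. They are given at Visit 1, and the daily hormone stopped "prior to their next visit (Visit 1") is pre-study supply, so no study-drug lag precedes them.

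**Lag counted from the end of the last dosing interval.** This follows the +1/+7 day convention of SAP 6.5.3, taken as 24 h for Genotropin and 168 h for somatrogon.

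- Sequence 1: 168 + 24 − gap = 192 − gap = 180 / 156 / 132 h.
- Sequence 2: 168 + 168 − gap = 336 − gap = 240 / 168 / 96 h.

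Under this start the overlap is substantial in both directions. Early Genotropin events in Sequence 2 could then be counted under somatrogon.

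**Effect on counts.** Take the lag from the last dose and an event confined to the overlap window after the first somatrogon dose, with incidence r in both sequences and 45 + 45 subjects.

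| Attribution | Somatrogon | Genotropin | Difference |
|---|---|---|---|
| By drug being taken | 90r/90 = r | 0 | r |
| Counted under both | 90r/90 = r | 45r/90 = r/2 | r/2 |
| Genotropin only (worst case) | 45r/90 = r/2 | 45r/90 = r/2 | 0 |

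The documents give no r. For assumed values of 2%, 10% and 20%, Genotropin gains 1, 5 and 10 percentage points under either misattribution. Somatrogon falls to 1%, 5% and 10% only in the worst case. A subject who has the same event again later on somatrogon would still be counted there.

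**The case against.** The strongest reply is that the rule was never meant to reach into the next period. It speaks of a break in treatment or the end of treatment. A child who has just injected somatrogon is in neither, and the corresponding period could mean the one in which the event occurs. On that reading the overlap is zero. SAP 4 also analyses the Safety population by the intervention actually received. In addition, SAP 3.5 and 6.6.1 refer to the sponsor's safety rulebook and CaPS, which may cut the lag at the next dose.

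Part of this stands. The no-overlap reading is possible, so misattribution is a risk in the wording, not a certainty. The other two arguments do not settle the matter. Analysis by intervention received says which drug a subject took, not which drug owns an event that falls in two windows. The external standards are not reproduced, and nothing in the documents shows that they override the lag that the SAP itself sets.

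A reader might infer that half of the first-dose somatrogon reactions would be lost to Genotropin. The documents do not support that as the expected result. Emergence is judged per treatment, so such an event also qualifies under somatrogon, and double counting is at least as likely. The somatrogon count would then be complete and only the Genotropin count inflated. A reader might also infer that Sequence 2 is essentially untouched, but that holds only if the lag starts at the last dose.

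The consequence is also partly recoverable. SAP 5 lists all data by sequence, subject and time, and Visit 4 has inquiries on both sides of the injection.

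**Conclusion.** The point holds as a defect in the wording of the attribution rule. As written, the rule lets one drug's effective duration run into dosing with the other, and it does not say how an event in both windows is counted. With the lag from the last dose, the overlap is 108 to 156 h in each Sequence 1 subject who switches within the window (at most about 45 of 90, fewer if some stop before Period II), and 0 to 72 h in Sequence 2. With the lag from the end of the dosing interval, it is 132 to 180 h and 96 to 240 h.

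The effect is confined to descriptive per-drug counts of treatment-emergent events. There is no hypothesis test on them and no effect on the primary endpoint. Halving of somatrogon counts is a worst case. It requires attribution to Genotropin only, events confined to the overlap window, and equal incidence in the two sequences. The correction is worth making because the same data could give different adverse event tables for the drug that the safety objective is about.

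**What to change.** Amend SAP 3.5.1 as follows:

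1. State where the lag starts, consistently with SAP 6.5.3. If it starts at the last dose, also say how events are assigned when the Sequence 2 gap exceeds 7 days; at the 10-day limit, 240 − 168 = 72 h fall in neither window.
2. End the Period I effective duration at the earlier of 7 days after that starting point or the first Period II dose.
3. Attribute events with onset after the first Period II dose to the Period II treatment only.
4. For events on the Visit 4 date, use the inquiries before and after injection to place the onset, and state a default where they cannot.

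The cost is SAP text and adverse event flag programming; no new data are needed. The drawback is that a late effect of the Period I drug may be credited to the Period II drug. A listing, by sequence, of events in the first 7 days of Period II would show this.
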